## **2.4. Study Design**

Observational feasibility. To determine if discharged COVID-19 patients with PICS symptoms are willing and able to navigate the technology necessary to participate in a virtual outpatient clinic. To determine if a multidisciplinary group of professionals, who are licensed in the state where the participant lives, familiar with PICS, are able to interpret information obtained from virtual visits and patient self-reported surveys to make recommendations for future care based on baseline and changes in patient symptoms over time. To determine the ease of receiving and receptiveness of primary care physicians to a summary of clinic recommendations. To determine if the PICS symptoms and patient characteristics of patients with an ICU stay due to COVID-19 are similar to those reported in the literature of non-COVID-19 patients.

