## 1. SYNOPSIS

[figure not shown]
Study Title	COVID-19 Virtual Post Intensive Care Syndrome (CoV-PICS) Clinic: Modern, Convenient and Practical Recovery Care.
Objective	To determine if discharged COVID-19 patients with PICS symptoms are willing and able to navigate the technology necessary to participate in a virtual outpatient clinic (feasibility and acceptance). To determine if a multidisciplinary group of professionals, familiar with PICS, are able to interpret information obtained from virtual visits and patient self-reported surveys to make recommendations for future care based on baseline and changes in patient symptoms over time (feasibility). To determine the ease of receiving and receptiveness of primary care physicians to a summary of clinic recommendations (feasibility and acceptance). To determine if the PICS symptoms and patient characteristics of patients with an ICU stay due to COVID-19 are similar to those reported in the literature of non-COVID-19 patients.
Study Period	Planned enrollment duration: Aug 2020 – Feb 2021  Planned study duration: Aug 2020 – Aug 2021
Number of Patients	80, adult (minimum age 18, no maximum)
Study Treatment	None
Study Design	Observational feasibility trial
Inclusion and Exclusion Criteria	
Inclusion Criteria:
 
 
1. Patients who are at least 18 years of age
 
2. COVID-19 diagnosis with a stay in the intensive care unit at BJH
 
3. Missouri resident
 
 
Exclusion Criteria:
 
 
1. Severe cognitive deficits or dementia prior to hospitalization
 
2. Long-term resident of a skilled nursing facility prior to admission
 
3. Non-English speaking (will not have an interpreter available)
 
4. Hospice or Comfort Care at discharge
 
5. No plans to return to some degree of independent living at the time of discharge
 
6. Pregnant or a prisoner at the time of discharge
 
7. Blind or deaf
 

CONFIDENTIAL: This document is the intellectual property of [name]. Acceptance of this document constitutes the agreement by the recipient that no unpublished information contained herein will be published or disclosed without prior written approval.

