function persist months to years after ICU discharge and are also associated with decrease ability to perform ADLs, as well as, reduced quality of life. There is strong evidence that patients with delirium while in the ICU may suffer from cognitive impairments long after they are discharged. Delirium is a common condition resulting from critical illness. This is particularly true in patients who require increased sedation and prone positioning to improve oxygenation, such as COVID-19 patients with ARDS. While receiving these medical interventions, patients often are unable to have clear memories leading to altered and sometimes frightening delusions from delirium.

Anxiety, post-traumatic stress disorder and depression (70%, 10-50%, and 30%, of survivors respectively) are the major mental illnesses noted in ICU survivors 12 months after discharge. Theoretically, these percentages may be even higher in patients with COVID-19 disease who may experience exacerbated feelings of emptiness, due to separation and isolation from family and friends, a breakdown of their social network, as well as the uncertainty about their diagnosis.

Prevention of PICS includes the incorporation of the ABCDEF bundle (assessment, prevention and management of pain; both spontaneous awakening and breathing trials; choice of analgesia and sedation; coordination of care and communication; delirium assessment, prevention and management; early mobility and exercise; and family engagement), widely known as the bundle that addresses the risks of sedation, delirium and immobility. Both inactivity and malnutrition may exacerbate ICU-AW through skeletal muscle mass, strength and function loss. ICU diaries completed by staff and family members for the patient provide a description of experiences during ICU care. The diary may help to prevent PICS by improving the orientation of the patient and alleviating anxiety, depression and PTSD symptoms.

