## 2.2 Objective

- Evaluate discharged ICU COVID-19 patients’ involvement in, and acceptance with virtual CoV-PICS clinic visits.
- Test the design of a multi-professional telehealth outpatient CoV-PICS clinic for effective care processes that evaluate impairments in physical, cognitive and mental health function in patients with COVID-19 disease.
- Determine the feasibility and acceptance of Primary Care Physicians regarding information provided and communication process from the CoV-PICS clinic.
- Determine if the PICS symptoms experienced by COVID-19 patients are similar to historically reported symptoms in non-COVID 19 patients with PICS.

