### **2.4.6.4 Secondary Outcome Measures**

[figure not shown]
Secondary outcomes: (to compare patient characteristics to historical non-COVID-19 patients with PICS)

1. ICU Memory Tool® (measures recall and aids in our understanding of the quality of life)
2. PROMIS®29 Profile (measures anxiety, depression, fatigue, pain, physical function, sleep and ability to participate in social roles),
3. MOCA-5 minute® (measures cognitive function),
4. Katz and Lawton® (measures activities of daily living),
5. PG-SGA short form® (screens for malnutrition risk),
6. Five-time sit-to-stand, and Two-minute step test.

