### **2.4.6.5 Statistical Methods**

Descriptive statistics will be used to summarize the data. Continuous variables will be reported as medians and interquartile ranges or means and standard deviations as appropriate. Categorical variables will be reported as frequencies and percentages. Changes in the scores or times of the ICU Memory Tool®, PROMIS®29 Profile, MOCA-5 minute, Katz and Lawton®, PG-SGA short form®, Five time sit-to-stand and Two-minute step test, from hospital discharge to 3- and 6-month post discharge will be estimated using the Wilcoxon Signed Rank Test (non-parametric alternative to t-test) and compared across different categorical variables (e.g. age, gender, discharged directly to

CONFIDENTIAL: This document is the intellectual property of [name]. Acceptance of this document constitutes the agreement by the recipient that no unpublished information contained herein will be published or disclosed without prior written approval.

home, 30-day readmission) using ANOVA and continuous variables (e.g. APACHE IV, ICU length of stay) using ANCOVA.

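### The fourth objective asks whether COVID-19 PICS symptoms are similar to the published non-COVID-19 picture, but no planned analysis uses an external value, so the plan cannot support that verdict

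*Combined protocol and SAP*

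**What the plan says.** The similarity question is an objective in the Synopsis, in section 2.2 and in section 2.4. Section 2.4 asks whether symptoms and characteristics "are similar to those reported in the literature of non-COVID-19 patients"; section 2.2 asks whether symptoms "are similar to historically reported symptoms in non-COVID 19 patients with PICS". Section 2.4.6.4 gives the purpose of the secondary outcomes as "to compare patient characteristics to historical non-COVID-19 patients with PICS".

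Section 2.4.6.5, repeated in the Synopsis, plans three things:

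- descriptive summaries of the cohort;
- changes in instrument scores or times "from hospital discharge to 3- and 6-month post discharge will be estimated using the Wilcoxon Signed Rank Test";
- comparison of those changes across patient factors, by ANOVA for categorical factors and, for "continuous variables (e.g. APACHE IV, ICU length of stay) using ANCOVA".

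The Synopsis gives the number of patients as "80, adult (minimum age 18, no maximum". Section 2.4.6.6 describes a convenience sample with a power analysis only after the fact. The background (section 2.1.1) cites 12-month rates in ICU survivors: "Anxiety, post-traumatic stress disorder and depression (70%, 10-50%, and 30%, of survivors respectively".

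**The concern.** An objective that asks whether two populations are alike needs a reference value, a measure at a stated time, and a rule for reading the result. The plan gives none of these. Every inferential analysis in section 2.4.6.5 compares the cohort with itself, over time or across its own subgroups.

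The answer will therefore be improvised after the data are seen, with a free choice of literature source, time point and cut-off. The published report could then state that PICS after COVID-19 resembles PICS after other critical illness, and no prespecified analysis would stand behind that statement. Limited precision and unlike populations add to the problem, because either can make real differences hard to see or create apparent agreement.

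**Working it through.** **1. Objective against analysis.** Setting sections 2.2, 2.4 and 2.4.6.4 beside 2.4.6.5, I looked for any planned step with an external input. Descriptive summaries use cohort data only. The Wilcoxon signed rank test pairs each patient with himself or herself. ANOVA and ANCOVA use factors such as age, readmission, APACHE IV and ICU stay, all measured within the cohort. No step uses a literature figure.

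**2. The planned number.** No alpha, power, margin or effect size accompanies 80, so it cannot be reproduced as a power calculation. The only sample-size arithmetic is accrual: 29 × 0.50 = 14.5, the plan's roughly 15 a month. Over 6 to 7 months that gives 14.5 × 6 = 87 to 15 × 7 = 105. No precision target lies behind 80.

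**3. Precision at n = 80.** Assumptions: the outcome is dichotomised (the plan analyses scores and times and gives no cut-offs), and the literature rate p is 30%, 50% or 70%, in line with the cited 30%, 50% to 70% and 70%.

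Half-width of the 95% CI = 1.96 × √(p(1−p)/n):

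- n = 80: 1.96 × √(0.21/80) = 10.0 points at 30% or 70%; 1.96 × √(0.25/80) = 11.0 points at 50%.
- n = 60: 11.6 and 12.6 points. n = 40: 14.2 and 15.5 points.

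**4. Chance of missing a true difference.** Further assumptions: the literature rate is a fixed number, and the test is a two-sided 5% exact binomial test. With n = 80 the result is non-significant for 16 to 32 events against 30%, 31 to 49 against 50%, and 48 to 64 against 70%. The miss probability is the binomial probability of those counts under the true rate. Each cell gives the true rate lower / higher than the literature rate:

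| Literature rate | 10 points | 15 points | 20 points |
|---|---|---|---|
| 30% | 54.5% / 54.8% | 13.8% / 21.6% | 0.5% / 4.6% |
| 50% | 63.1% / 63.1% | 27.6% / 27.6% | 5.9% / 5.9% |
| 70% | 54.8% / 54.5% | 21.6% / 13.8% | 4.6% / 0.5% |

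Eighty is planned enrolment, and section 2.4.1 withdraws patients who do not return repeat surveys. The plan gives no dropout rate. With an assumed 60 analysed, the ranges become 55–74%, 18–44% and 2–16%. With 40 they become 71–79%, 39–57% and 10–32%.

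**5. If the literature rate has its own sampling error.** The cited studies whose sizes are given have 34, 72 and 109 patients. They are not the sources of the mental-health rates and serve only to show scale. With 80 patients against samples of those sizes (normal approximation), a 10-point difference is missed 78–84%, 70–77% and 66–73% of the time. For 20 points the figures are 27–50%, 12–29% and 7–21%.

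**6. Are the rates like for like?**

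- *Population.* The cited rates describe ICU survivors. Section 3.3 seeks consent only when the telephone screen points to possible PICS, so this cohort is selected on symptoms.
- *Time.* The cited mental-health rates are at 12 months. Symptom surveys are last sent 22 weeks after the initial visit (section 2.4.1). Allowing 10 weeks from discharge to screening (section 2.4.6.6) and 18 days to the initial visit, and assuming no lag between screening and consent, this is 22 + 10 + 18/7 = 34.6 weeks after discharge, well short of 52.
- *Measure.* Section 2.4.6.4 lists no PTSD instrument. The six-minute walk and return-to-work figures in section 2.1.1 have no counterpart among the outcomes.
- *Width.* The PTSD range spans 40 points. An observed 30% with a 95% CI of 20% to 40% would lie wholly inside it, so agreement with the range would say little.

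**The case against.** The best defence is that this is an observational feasibility study with a convenience sample, that the comparison is secondary, and that descriptive statistics are planned. Section 3.4 says only that symptoms can be set against earlier reports. On that view a formal equivalence design would be out of proportion. This stands as an argument against demanding an equivalence margin, and a descriptive comparison would be enough. It does not close the gap, because summarising the cohort is not comparing it, and the objectives ask for a determination.

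Three stronger readings are tempting, and the documents do not support them.

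- A reader might infer that the plan will treat a non-significant test as proof of similarity. Section 2.4.6.5 plans no test against historical values, so that is a possible misuse and not the written method.
- A reader might infer that a finding of no difference at n = 80 would often be wrong. More than half of true differences are missed at about 10 points, but at most 6% at 20 points against a fixed rate. These are also miss rates given an assumed difference, not the probability that a conclusion of similarity is false.
- A reader might infer that a 95% CI from 80 patients can never fall within ±10 points of the literature rate. With no true difference, that is so at 30%, 50% and 70%. At 10%, the lower end of the cited PTSD range, a Wald interval does so with probability 0.79, and at 20% with probability 0.22.

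**Conclusion.** The point holds as a gap between objective and analysis. The plan promises a verdict on similarity and contains no analysis that could support one. This rests on the text alone and needs no assumption.

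The size of the precision problem is conditional. With a dichotomised outcome, a fixed literature rate of 30% to 70% and a two-sided 5% exact test, 80 patients miss a 10-point difference 55–63% of the time, a 15-point difference 14–28% and a 20-point difference 0.5–6%. The plan states none of these conditions. Fewer analysed patients, or a literature rate with its own error, make the figures worse.

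The mismatch in population and timing matters independently of sample size. Even an interval lying inside a margin fixed in advance would not by itself show similarity, because selection on symptoms or earlier assessment could produce the agreement.

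**What to change.** - Reword the fourth objective in the Synopsis and in sections 2.2 and 2.4 as: describe PICS symptoms and compare them descriptively with published figures.
- Add a table to section 2.4.6.5. For each outcome with a published counterpart, give the study estimate at a named assessment round with its 95% CI, beside the literature value, its source population and its time point. Name the literature values, and any cut-off needed to match them, before the data are examined.
- State the selection by telephone screen and the difference in follow-up time next to the table.
- State that similarity will not be concluded from overlapping intervals or from a non-significant difference.

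The cost is one paragraph, one table and the work of choosing literature values; no extra patients or visits are needed. The study gives up a claim of similarity, and some domains will have no usable comparator.

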### **2.4.1 Study Procedures**

[figure not shown]
Study Procedures – Patient and PCP involvement	
Consent	Verbal consent is being sought. RC will be in a private space and obtain consent. All visits with the patient will be “virtual”.
Chart Review	Once patient consent is obtained, a prospective or retrospective chart review (depending on availability of research team members) will be conducted to obtain several data points (see attached).
Day 1	RC: Add patient to enrollment log: Study ID, first name, 3 letters of last name, MRN#, hospital discharge date, date returned home (if different from discharge date), and patient preferred email and phone number. If patient consents, PCP name, office phone number and fax number. This will be in a password protected Excel file available only to research team members.
Day 1	RC: Document date/time of consent, upload pdf of note to RedCap

CONFIDENTIAL: This document is the intellectual property of [name]. Acceptance of this document constitutes the agreement by the recipient that no unpublished information contained herein will be published or disclosed without prior written approval.

[figure not shown]
Day 1	
RC: Patient emailed a copy of the verbal consent, as well as, an information sheet, including a timeline for the study and “what to expect” and “what not to expect”.
 
What to expect: Timeline for study, Initial surveys, follow up surveys at 3 and 6 months, team visits (when – at minimum every 12 weeks; time commitment – 60-75 minutes), bi-weekly touch base email by RCs, individual visits with team members if warranted, summary of team recommendations after each visit, potential contact from PCP (if patient consented for information to be shared) and contact information for RC and PI for any questions or concerns throughout the study period. All providers engaging in telehealth visits will be licensed in the state where the participant lives.
 
What not to expect: Clinic physicians or other providers to write prescriptions, order lab tests or perform any treatments

Day 1-2  Week 10 post initial visit And Week 22 post initial visit	
RC: If patient not enrolled in MyChart or has forgotten how to access, call patient and walk them through obtaining access. Direct link (attached to the patient’s study ID) will be emailed or texted (per patient preference) to access the following surveys, requesting one week turn-around time:
 
ICU Memory Tool® (measures recall and aids in our understanding of quality of life)
 
PROMIS®29 Profile (measures anxiety, depression, fatigue, pain, physical function, sleep and ability to participate in social roles)
 
MOCA-5 minute® (measures cognitive function)
 
PG-SGA short form® (screens for malnutrition risk)

Day 2-9  Week 11 and Week 23 post initial visit	
RC: Will send form email from PI to PCP (if patient agreed to share information) providing an overview of the study (see attached)
 
RC will obtain notice from RedCap when surveys opened. RC will check completeness of survey responses. If surveys not completed within 5 days, send reminder email. If not completed in 7 days, call patient offering to administer surveys over the phone.

Day 11  Week 11 and Week 23 post initial visit	
RC: If patient does not complete surveys within 7 days of receipt and has not responded to phone calls; considered an enrollment fail (start of study) or withdrawal from study (repeat surveys), document on enrollment log.

Day 2-11  Week 11 and Week 23 post initial visit	
RC: If surveys completed, send thank you email. Email and/or call patient to schedule first virtual visit. Email link to research team members for them to review responses in RedCap.

Day 9 – 18  Week 12 and Week 24 post initial visit	
RC: Schedule initial 60-75 minute virtual assessment based on MD schedule. Email all team members to obtain availability in non-physician visit time. Send outlook calendar appointments to team members. All providers engaging in telehealth visits will be licensed in the state where the participant lives.

1-2 days before virtual team visit	
RC: Send reminder email to research team members who will be on the visit. Send agenda for call – member/time slot. Send instructions/link for team members to join the virtual visit. Email the patient the instructions on how to access the virtual appointment in MyChart or the HIPPA approved WashU ZOOM link.

CONFIDENTIAL: This document is the intellectual property of [name]. Acceptance of this document constitutes the agreement by the recipient that no unpublished information contained herein will be published or disclosed without prior written approval.

30 min before each virtual team visit	RC: Email/call patient to address any concerns/questions regarding accessing virtual visit. RC will be “host” of the link for the visit.
Time of virtual team visit	RC: Send text to research team that patient has successfully entered the virtual visit.
During virtual team Visit	RC will function as timekeeper – send “chats or texts” to research team members to keep them on time. Team members will speak one at a time, with other members on mute. MD will start with introduction and overview that summary of recommendations after the visit will be sent to the patient’s PCP and the patient, emphasizing the patient and the PCP will be responsible for implementing and monitoring recommended treatments. Each professional will follow with introduction/any additional questions. The physical therapist and occupational therapist will go last to complete the following if the patient agrees/is able: Katz and Lawton® (measures activities of daily living) Five time sit-to-stand Two minute step test All providers engaging in telehealth visits will be licensed in the state where the participant lives.
1-3 days post virtual team visit	Team Members: responsible for documenting in EPIC their note/summary within 2 days of visit RC: Email patient summary of recommendations are available in MyChart for patient to access. Email PCP that summary is available in MyChart, or fax summary if PCP does not have access to MyChart. Clinic MD may choose to contact PCP personally regarding patient evaluation if they deem necessary.
2, 4, 6, 8, 10 weeks post initial and second virtual team visit	RC: Phone call to patient – What recommendations have been implemented? Any questions for any member of the research team? Any team member: may touch-base with the patient or treating professional (home physical therapist) if recommendations have been implemented by the PCP (e.g. physical therapy, change in medication, change in diet) to determine if they have any questions regarding the treatment initiated. If team member desires a virtual visit with patient – RC will host.
Week 25 - 26	RC: Send final surveys to patient via link. An email with a link will also be sent to their PCP – at the start of their survey a statement will be made clearly stating if they complete the survey they are consenting to the study. The final survey tools sent will include: FIM® (feasibility of intervention measure), IAM® (intervention appropriateness measure) and the AIM® (acceptance of intervention measure). If surveys not completed within 5 days, send reminder email. If not completed in 7 days, if patient – phone call offer to administer surveys over the phone; if PCP send 2 nd email reminder. If the PCP does not complete, will consider denial to participate (document on enrollment form).
Week 25 - 26	RC: Once final surveys are completed email patient informing them their participation in the study is now completed, thanking them for their time and offering any final comments regarding the feasibility of the clinic may be emailed.
RC: research coordinator, PI: principle investigator, PCP: primary care physician	

CONFIDENTIAL: This document is the intellectual property of [name]. Acceptance of this document constitutes the agreement by the recipient that no unpublished information contained herein will be published or disclosed without prior written approval.

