## **2.4.3 Pre-Study Period**

## **2.4.4 Study Period**

### **Methods:**

## **2.4.6 Observations and Measurements**

### **2.4.6.3 Primary Outcome Measures**

Primary outcomes:

1. Patient adherence and determination of feasibility and acceptance with the virtual clinic and telehealth visits based on the FIM® (feasibility of intervention measure), IAM® (intervention appropriateness measure) and the AIM® (acceptance of intervention measure)
2. Patient attendance record
3. Number of on-time arrivals to the virtual visit
4. Number of patient successfully completed online questionnaires after initial training.
5. Patient primary care or clinic physician feedback using the tools in #1 and open ended comments.

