#### **2.5.2 Premature Discontinuation**

Subjects will be withdrawn if the investigator decides that discontinuation is in the best interest of the subject, inactivity by the subject or the subject requests withdrawal from the study.

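### The acceptability scales are scheduled only at weeks 25-26, after two points at which non-responders are withdrawn, so the ratings will rest mainly on patients who stayed

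*Combined protocol and SAP*

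**What the plan says.** - **Scales.** Section 2.4.6.3 bases the first primary outcome on FIM, IAM and AIM. In the schedule of section 2.4.1 they appear in one row, weeks 25-26: "The final survey tools sent will include: FIM® (feasibility of intervention measure), IAM® (intervention appropriateness measure) and the AIM® (acceptance of intervention measure". The survey packets at days 1-2 and at weeks 10 and 22 hold other instruments (ICU Memory Tool, PROMIS-29, five-minute MoCA, PG-SGA short form).
- **Non-response rule.** Section 2.4.1 provides a reminder email at 5 days and, at 7 days, a call offering to take the survey by phone. It then deals with the patient who still has not completed it and "has not responded to phone calls; considered an enrollment fail (start of study) or withdrawal from study (repeat surveys), document on enrollment log". The rule applies at day 11 and at weeks 11 and 23 after the initial visit.
- **Other exits.** Section 2.5.2 also withdraws patients in their best interest as judged by the investigator, or for "inactivity by the subject or the subject requests withdrawal from the study". Inactivity is not defined.
- **Contacts in between.** The coordinator phones patients "2, 4, 6, 8, 10 weeks post initial and second virtual team visit". The calls cover which recommendations have been acted on and any questions for the team. Patients are invited to comment on the clinic only after finishing the final surveys.
- **Other primary outcomes.** These include an attendance record, "Number of on-time arrivals to the virtual visit" and "Number of patient successfully completed online questionnaires after initial training". Section 2.4.6.5 says "Descriptive statistics will be used to summarize the data" and promises percentages, but names no denominator.

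**The concern.** The study asks whether patients accept a virtual clinic. Under the schedule, a patient who stops engaging after one or two visits leaves the study before the only point at which the clinic is rated. A missing rating is therefore tied to disengagement, which is part of what the study measures. Attendance and survey completion will show that the patient stopped; they will not show what the patient thought of the clinic. If those who leave think less of it than those who stay, the reported acceptability is too high. A rating that was never requested cannot be recovered at analysis.

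**Working it through.** The plan gives no figure to reproduce: there is no expected loss rate, no target for the scales and no cut-off for a favourable rating. The check is the order of events, followed by an illustration.

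**Order of events (section 2.4.1, weeks after the initial visit)**

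1. Initial team visit, then calls at weeks 2, 4, 6, 8 and 10.
2. Week 10: repeat surveys. Week 11: non-responders withdrawn. Week 12: second visit.
3. Further calls 2 to 10 weeks after the second visit.
4. Week 22: repeat surveys. Week 23: non-responders withdrawn. Week 24: third visit.
5. Weeks 25-26: FIM, IAM and AIM.

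Two withdrawal points fall between first use of the clinic and the only rating. Day 11 is a third loss point, but it precedes the first visit, so those patients have no clinic experience to rate. All five calls of the first set come before week 11.

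**Share of first-visit patients without a rating**

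Let L be the loss at each of weeks 11 and 23 (assumed equal) and s = 1 - L. If everyone still in the study replies, the unrated share is 1 - s².

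- L = 5%: 1 - 0.95² = 0.0975, about 10%.
- L = 10%: 1 - 0.90² = 0.19, or 19%.

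In patients, using the planned 80 (Synopsis):

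- If 80 reach the first visit: 80 × 0.0975 = 7.8, or 80 × 0.19 = 15.2.
- If 80 are consented and the same share is lost at day 11: 80 × 0.95 × 0.0975 = 7.4, or 80 × 0.90 × 0.19 = 13.7.

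**Effect on a reported percentage**

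Suppose 80% of those rated are favourable (assumed, with a cut-off the plan does not define). The bounds over all first-visit patients run from 0.8s² to 0.8s² + (1 - s²):

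- L = 5%: 0.722 to 0.8195, about 72% to 82%.
- L = 10%: 0.648 to 0.838, about 65% to 84%.

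The overstatement is (1 - s²) × (favourable share in stayers - favourable share in leavers). With 80% and an assumed 50%, it is 0.0975 × 0.30 = 0.029 or 0.19 × 0.30 = 0.057, about 3 or 6 percentage points.

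**What an early rating would do**

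If a fraction c of later leavers had already given a rating, the share with none falls to (1 - s²)(1 - c). With c = 50% (assumed), that is 0.0975 × 0.5 = 0.049 or 0.19 × 0.5 = 0.095.

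**The case against.** - **The text does not bar withdrawn patients from the final survey.** This is correct. The weeks 25-26 row says that patients are sent the surveys and carries no such restriction. A reader might take it as stated that leavers are never asked; it is an inference from withdrawal from the study and from the absence of any later contact for these patients. It remains the natural reading, and one sentence would settle it if something else is meant. The consent script, phone screen and data list are attachments not available here.
- **Loss may be small.** Withdrawal needs both an incomplete survey and no response to calls, after a reminder and an offer of phone completion, in a study with ten scheduled calls per patient. A reader might push the formula to 30% loss per round, where 1 - 0.7² = 51% would be unrated. Nothing in the documents supports that rate, and nothing establishes 5% or 10% either.
- **Asking at withdrawal comes too late.** Those withdrawn under this rule have just not responded to email and phone. This stands, and it is why the early rating should be the main remedy.
- **Disengagement is visible anyway.** Adherence, attendance and online completion are themselves primary outcomes and withdrawals are logged, so a reader can see how many ratings are missing. That is true, but the opinions of those patients are still absent.
- **Missing denominators.** A reader might infer that attendance, punctuality and online completion could be made to look good after the event. The analysis is descriptive, has no success threshold, and rates over all consented patients can be rebuilt from the enrollment log. Whether a day-11 enrollment fail belongs in such a rate is arguable. This is a reporting note.

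**Conclusion.** The concern holds in limited form. Followed as written, the plan obtains acceptability ratings mainly from retained patients, and the loss of ratings is linked to disengagement. The likely direction is favourable to the clinic, on the assumption that leavers would on average rate it lower than stayers. The size cannot be determined: the loss rates, the 80% and 50% favourable shares and the 50% early reply rate are all assumptions, and the roughly 10% and 19% unrated are illustrations. The documents do not support a claim that acceptability will be seriously overstated. They do support a low-cost improvement, which has to be made prospectively because an unrequested rating cannot be rebuilt.

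**What to change.** 1. **Main change, section 2.4.1.** Collect FIM, IAM and AIM once from every patient who attended the first visit, with the coordinator call already scheduled two weeks later. Keep the weeks 25-26 rating as the main one. Use the early rating only where no later one exists, and report it separately.
2. **Secondary change, sections 2.4.1 and 2.5.2.** At withdrawal, ask patients who have not refused contact for one reason for leaving and, if they are willing, a rating. Expect low yield among non-responders. State whether withdrawn patients are sent the final surveys.
3. **Reporting, section 2.4.6.5.** Give the number rated out of all first-visit patients, with worst-case and best-case bounds for those unrated.
4. **Minor reporting note.** Give attendance, on-time arrival and online completion over all consented patients as well as over scheduled visits, with enrollment fails shown separately.

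The cost is one extra short survey per first-visit patient at an existing call and, in the illustration, about 7 to 15 exit contacts by the existing coordinator. Section 2.4.1 has "Patient emailed a copy of the verbal consent, as well as, an information sheet" with the study timeline on day 1, so the verbal consent and that sheet may need a small amendment and IRB approval. An early rating reflects a single visit, and the reported result may be less favourable.
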